## 7 STUDY POPULATION

### 7.1 Inclusion Criteria

For inclusion in the study, patients must fulfill all of the following criteria:

1. Provision of signed and dated, written informed consent before any study specific procedures, sampling and analyses
2. Aged at least 18 years
3. Histological or cytological confirmation of advanced and/or metastatic stage IIIB/IV NSCLC
4. Radiological documentation of disease progression while on a previous continuous (at least 30 days) treatment with an EGFR TKI monotherapy (including, but not limited to, osimertinib, afatinib, dacomitinib, gefitinib, or erlotinib). All patients must have documented radiological progression on the last treatment administered prior to enrolling in the study
5. [REDACTED]

[REDACTED]  
[REDACTED]  
[REDACTED]  
[REDACTED]

World Health Organization  
(WHO) criteria, after treatment of an EGFR TKI

6. Adequate bone marrow reserve or organ function as demonstrated by all of the following laboratory values:
  - Absolute neutrophil count (ANC)  $> 1.5 \times 10^9$  cells/L (without growth factor support for 2 weeks prior to testing)
  - Platelet count  $> 75 \times 10^9$  cells/L (without transfusion or growth factor support for 1 week prior to testing)
  - Hemoglobin  $> 9.0$  g/dL (without transfusion or growth factor support for 2 weeks prior to testing)
  - Alanine aminotransferase  $\leq 2.5$  times the upper limit of normal (ULN)
  - Aspartate aminotransferase  $\leq 2.5$  times the ULN
  - Total bilirubin  $\leq 1.5$  times the ULN

- Creatinine  $\leq$ 1.5 times the ULN, creatinine clearance  $\geq$ 50 mL/min (measured or calculated by Cockcroft-Gault equation). Confirmation of creatinine clearance is required when creatinine is  $>$  1.5 times the ULN

7.

[REDACTED]

8. Patients must have measurable disease per RECIST v1.1 presented
9. Eastern Cooperative Oncology Group (ECOG) performance status of 0 to 1
10. Females, if of child-bearing potential, should be using adequate contraceptive measures, should not be breastfeeding, and must have a negative pregnancy test result prior to start of dosing, or must have evidence of non-child-bearing potential by fulfilling one of the following criteria at Screening:
  - Post-menopausal defined as aged more than 50 years and amenorrhoeic for at least 12 months following cessation of all exogenous hormonal treatments
  - Women aged fewer than 50 years will be considered postmenopausal if they have been amenorrhoeic for 12 months or more following cessation of exogenous hormonal treatments and with Luteinizing Hormone (LH) and Follicle Stimulating Hormone (FSH) levels in the post-menopausal range as defined by the institution
  - Documentation of irreversible surgical sterilization by hysterectomy, bilateral oophorectomy, or bilateral salpingectomy but not tubal ligation
11. Male patients should be willing to use barrier contraception (i.e., condoms)

## 7.2 Exclusion Criteria

An individual who meets any of the following criteria will be excluded from participation in this study:

1. Treatment with any of the following:
  - An EGFR TKI, including but not limited to osimertinib, afatinib, dacomitinib, gefitinib, or erlotinib within 8 days of the first dose of study treatment.
  - Small molecule targeted inhibitor other than EGFR inhibitor class, or cytotoxic chemotherapy within 14 days; biologic anticancer medicine (cytokines or antibodies, etc.) within 28 days (before the initiation of BBT-176 treatment) for the systemic treatment of advanced NSCLC
  - Major surgery (excluding placement of vascular access) within 4 weeks of the first dose of study treatment
  - Radiotherapy with a limited field of radiation for palliation within 1 week of the first dose of study treatment
  - Patients receiving radiation to more than 30% of the bone marrow or with a wide field of radiation within 6 weeks of the first dose of study treatment
  - Patients receiving CYP2C8 or P-gp strong inhibitor (see Appendix 4)
2. Any unresolved toxicities from prior therapy greater than NCI Common Terminology Criteria for Adverse Events (CTCAE v5.0) Grade 1 at the time of starting study treatment, with the exception of alopecia and Grade 2 neuropathy related to prior platinum-therapy
3. Spinal cord compression or brain metastases, unless asymptomatic and stable fulfilling one of following:
  - Not requiring active treatments prior to start of study treatment
  - Requiring stable dosing regimens of low-dose oral corticosteroid (up to 20 mg prednisone/day or equivalent) for at least 4 weeks prior to the first dose of study treatment
4. Even if the patient has progressed after EGFR TKI therapy, if there is a treatment proven to be effective, the patient should receive the treatment first. This includes cases where documented evidence of *MET* amplification, *HER2* mutation, or SCLC transformation exists and treatments or clinical trials that have been proven for the corresponding mutations are available.
5. Any evidence of severe or uncontrolled systemic diseases, including uncontrolled hypertension and active bleeding diatheses that in the Investigator's opinion makes it

[figure not shown]
undesirable for the patient to participate in the trial or would jeopardize compliance with the protocol, or active infection including hepatitis B, hepatitis C, and human immunodeficiency virus (HIV). Screening for chronic conditions is not required

6. Any of the following cardiac criteria:
  - Mean resting QTc interval (corrected by Fridericia's formula [QTcF]) > 470 msec obtained from average value of 3 electrocardiograms (ECGs), using the screening clinic ECG machine derived QTc value
  - Any clinically important abnormalities in rhythm, conduction or morphology of resting ECG (e.g., complete left bundle branch block, third degree heart block, second degree heart block, or PR interval of >250 msec)
  - Any factors that increase the risk of QTc prolongation or risk of arrhythmic events, such as heart failure (ejection fraction < 50%; for details refer to [Section 10.2.3.3](#)), hypokalemia, congenital long QT syndrome, family history of long QT syndrome or unexplained sudden death before the age of 40 years in first-degree relatives, or any concomitant medication known to prolong the QT interval
7. Past medical history of ILD, drug-induced ILD, radiation pneumonitis that required steroid treatment, or any evidence of clinically active ILD
8. Refractory nausea and vomiting, chronic gastrointestinal diseases, inability to swallow the study treatment, or previous significant bowel resection that would preclude adequate absorption of BBT-176
9. Involvement in the planning and conduct of the study
10. Judgment by the Investigator that the patient should not participate in the study if the patient is unlikely to comply with study procedures, restrictions, and requirements
11. Previous or concomitant malignancies at other sites, except effectively treated non-melanoma skin cancers, carcinoma in situ of cervix, ductal carcinoma in situ or effectively treated malignancy that has been in remission for more than 3 years and is considered to be cured
12. History or presence of hypersensitivity or idiosyncratic reaction to the study drug(s) or related compounds
13. History or presence of alcoholism or drug abuse within the past 2 years prior to the first dose

## 7.5        **Definition of Evaluable Patient (For Part 1 Dose Escalation Cohorts)**

An evaluable patient is defined as a patient who has completed minimum safety evaluation requirements during the first 21 days or has experienced a DLT during the first 21 days.

During Part 1 dose escalation cohorts, in the case that patients in the cohort are not evaluable, additional patients will be enrolled in the cohort.

Patients who are not evaluable might continue trial treatment upon agreement between Investigator and Sponsor, however the patient will not be considered for the evaluation of MTD.

## **8 STUDY TREATMENT AND DOSE MODIFICATIONS**

### **8.1 Study Treatment(s) Administration**

#### **8.1.1 Study Treatment Description**

BBT-176 is a competitive TKI that targets selected drug-resistant *EGFR* mutants, including C797S-triple mutation.

#### **8.1.2 Method of Assigning Patients to Treatment Groups**

For Part 1, the eligible patients will be assigned to the dose escalation cohorts first, and to exploratory cohorts if there are no available dose escalation cohorts.

An Interactive Web Response System (IWRS) system will be deployed to manage the supply of BBT-176 capsules to sites and to manage the dispensing of BBT-176 to patients.

The treatment medication assignment will be managed through an IWRS system. In addition, patient's screening, dose assignment, all drug dispensation visits, and EOT visit will be documented in the IWRS system.

Screening and treatment slots are assigned according to the cohort management plan. After the Sponsor (or designated CRO) has been notified by a site about a potential patient, the slot will be reserved to this site for a maximum of 7 calendar days. If the informed consent form (ICF) has not been signed by the potential patient within this time window, the slot will be opened up again for all recruiting sites.

Patients who meet the eligibility criteria and who have given their written informed consent will be entered into the study.

Before entering patients at the next dose level, it will be ensured that all patients at an ongoing cohort have completed the first cycle. Prior to inclusion of a new patient, the Investigator should confirm the respective dose with the Sponsor (or designated CRO).

#### **8.1.3 Dosing and Administration**

##### **8.1.3.1 Dosing and Meal Timing**

There is no meal restriction on BBT-176 dosing. Patients will take BBT-176 at home at about the same time every day, except on days with scheduled study visits including pre-dose PK sampling, patients should not take their dose of study medication at home in order to complete pre-dose PK plasma collection.

##### **8.1.3.2 Starting Dose and Dose Levels**

BBT-176 will be administered orally once daily at a starting dose of 20 mg in Cohort 1. The starting dose justification is described in [Section 6.2](#).

The dose-escalation scheme proposes [REDACTED] as shown in [Table 1](#).

[figure not shown]
[REDACTED]

[REDACTED]

[REDACTED]

[REDACTED]

[REDACTED]

In case 160 mg BID is assessed to be intolerable by the Safety Monitoring Committee, then 120 mg BID may be explored further. Dosage and frequency for Dose level  $\geq 2$  may be altered based on the PK, pharmacodynamics, and safety data obtained from previous dose level.

#### 8.1.3.3 Dose Escalation

##### **Bayesian Model-based Method for dose escalation:**

Bayesian model-based method will be used for the next dose recommendation for dose escalation. Dose-escalation of BBT-176 to determine the MTD will be guided by the mCRM using a BLRM following dose [REDACTED]

[REDACTED]

[REDACTED]

[REDACTED]

[REDACTED]

[REDACTED]

## Prior Distribution Specification

The prior distribution will be calculated based on:

1. Probability of DLT at [REDACTED] mg (starting dose): 0.05
2. Estimate of MTD: [REDACTED]

In the 28-days GLP toxicology study, the [REDACTED]

[REDACTED] therefore, patients [REDACTED] are not expected to show DLT.

Based on these, [REDACTED]

The [REDACTED]

[REDACTED]

[REDACTED]

[REDACTED] on these, [REDACTED]

[REDACTED]

[REDACTED]

[REDACTED]

[REDACTED]

[REDACTED]

The acceptable dose range is on a continuous scale between the minimum and maximum doses. The upper limit of the acceptable range is the largest dose whose probability of overdosing is less than the EWOC threshold. The lower limit of the acceptable range is the dose whose DLT rate is equal to the lower limit of the targeted toxicity interval.

When the acceptable dose range of the next cohort is recommended by the BLRM, the SMC will decide the next dose within the acceptable dose range or a lower dose than the lower limit. The SMC will consider the following for the dose decision:

- [REDACTED]
- [REDACTED]

Intermediate or lower dose levels, as long as they fulfil the EWOC criterion, may be recommended by the SMC and investigated if agreed upon between Investigator and Sponsor.

[REDACTED]

[REDACTED] will be applied  
to guide [REDACTED] The [REDACTED]

#### 8.1.3.4 RP2D Exploration

At the discretion of the Sponsor, once the RP2D has been provisionally established, [REDACTED] additional patients with molecularly defined biomarker may be enrolled and treated at that dose in order to further characterize safety, tolerability, PK, and efficacy, and to confirm its selection as the optimal dose to evaluate in Phase 2. RP2D exploration may be conducted in more than one cohort according to mutant types.

The [REDACTED]

#### 8.1.3.5

#### 8.1.3.6 Dose Reduction Criteria

In Part 1, no dose reduction is permitted in Cycle 1 without the Sponsor approval. If a patient in Part 1 is confirmed to have experienced a DLT in Cycle 1, then the Investigator, with the Sponsor approval, may do either of the following:

- Continue treating the patient at the next lower dose level evaluated, if the Investigator expects clinical benefit from further treatment, the toxicity is manageable, and the Investigator and the Sponsor's medical monitor (or designee) agree. A patient who receives a modified dose will be evaluated for safety at that dose level, but will not be counted towards the number of patients with DLTs at that dose level.
- Discontinue the patient from the treatment and the study.

[figure not shown]
Treatment with BBT-176 should be held until the toxicity resolves to  $\leq$ Grade 2. Dosing may then be resumed at either the same dose or the next lower dose level evaluated, per Investigator discretion. If treatment is resumed at the same dose, and the patient experiences the same

[figure not shown]
toxicity, the dose should be reduced following treatment hold and resolution of the event. If the patient continues to experience toxicity, a second dose reduction to a previously evaluated lower dose is permitted. Only two dose-reduction steps are allowed. If a patient continues to experience toxicity after two dose-reduction steps, or if dosing with BBT-176 is interrupted for >14 consecutive days due to toxicity, treatment should be discontinued, unless otherwise agreed upon between the Investigator and the Sponsor.

During Part 1, after Cycle 1, up to two dose reduction steps are allowed for each patient, if CTCAE Grade 3 or 4 toxicities are observed. The dose may be held or continued at the next lower dose level as described below.

For the RP2D exploratory cohort, the Investigators will have discretion to adjust dose in individual patients according to tolerability and safety from Cycle 1. Two dose reductions steps are allowed. If a patient continues to experience toxicity after two dose reduction steps, or if dosing with BBT-176 is interrupted for >14 consecutive days due to toxicity, treatment should be discontinued, unless otherwise agreed upon between the Investigator and the Sponsor. The dose may be increased, if the sponsor agrees, not exceeding MTD, when such concerns are resolved or mitigated. The Investigator may consult to the Sponsor about dose adjustment. Below table is an example. In case of not-specified adverse events, the Investigator and the Sponsor will discuss further and determined the adjusted dose according to available scientific literatures.

Table 2. Recommended Dose Adjustment Scheme

If a patient at the RP2D was required to reduce their dose level due to a non-drug-related toxicity, and the toxicity subsequently resolved, then the dose may be re-escalated back to the recommended dose, if tolerated.

## **8.2 Preparation, Handling, Storage, and Accountability**

### **8.2.1 Acquisition and Accountability**

The Investigator will maintain accurate records of the receipt of all study medications. In addition, accurate records will be kept regarding when and how much study medication is dispensed and used by each patient in the study. Reasons for deviation from the expected dispensing regimen must also be recorded. Study medication will be reconciled by the site. The Investigator agrees to provide sufficient access to study medication as required for the reconciliation process to be completed in a timely fashion.

### **8.2.2 Formulation, Appearance, Packaging, and Labeling**

BBT-176 is [REDACTED] The formulated BBT-176 contains citric acid and pharmaceutically acceptable excipients. For [REDACTED]

### **8.2.3 Product Storage and Stability**

Bottles containing BBT-176 should be stored at temperatures of 15°C to 30°C (59°F to 86°F), protected from high humidity and direct sunlight. The cap on the bottle should be tightly closed after each use and out of the reach of children.

### **8.2.4 Preparation**

No preparation is required for BBT-176.

### **8.3 Measures to Minimize Bias: Randomization and Blinding**

Randomization and blinding are not applicable to this non-randomized, open-label trial.

### **8.4 Study Treatment Compliance**

Adherence to administration of study treatment will be assessed by the amount of study treatment distributed versus the amount returned.

The appropriate number of capsules for 3 weeks treatment will be provided to patients to be self-administered at home. Patients will be asked to bring the remaining trial medication at the end of each cycle to the Investigator site for a compliance check. Remaining capsules will be counted by Investigator/site staff and recorded. Discrepancies between the number of capsules remaining and the calculated number of capsules the patients should have taken must be documented and explained. If the patient is eligible for further treatment, a new bottle of study drug will be dispensed.

In case a patient feels uncomfortable from the number of capsules, divided oral intake within 20 minutes is allowed.

Patient diary will also be assessed as a supplementary method for treatment compliance check.

In case a patient is unable to comply to the protocol-defined procedures due to public health policy, e.g., COVID-19 pandemic quarantine measures, the Investigator may delay physical examinations and laboratory examinations if the sponsor agrees. The Investigator should try every effort to communicate directly with the patient for safety follow-up, e.g., by telephone call or video conference. Such communications must be documented in eCRF.

### **8.5 Prior and Concomitant Therapy**

Prior medication will be recorded as part of the past medical history.

Concomitant therapy is defined as any medicinal product, prescribed or over-the-counter, taken by a patient other than the study drug. Use of concomitant medications will be recorded and reported. The Investigator will have discretion to prescribe medications which are recommended by public treatment guidelines to prevent or mitigate adverse events in cancer patients, e.g., nausea, vomiting, or diarrhea.

The Investigator will be responsible for preventive vaccination of the subjects according to the available public health policy of the jurisdiction where this clinical trial is being conducted. The Investigator may discuss with the Sponsor on individual decisions.

### 8.5.1 Emergency Procedures

Careful assessment of all patients with an acute onset and/or unexplained worsening of pulmonary symptoms (dyspnea, cough, fever) should be performed to exclude drug-induced ILD. Study drugs should be interrupted pending investigation of these symptoms. If drug-induced ILD is diagnosed, appropriate treatment should be instituted as necessary.

### 8.5.2 Restrictions

- Concomitant medications, or therapy to provide adequate supportive care, may be given as clinically necessary.
- Palliative radiotherapy may be given as described above.
- Additional experimental anti-cancer treatment and/or standard chemo-, immunotherapy, hormone treatment (with the exception of megestrol acetate for decreased appetite), or radiotherapy (other than palliative radiotherapy for symptom control) is not allowed concomitantly with the administration of study treatment.
- [REDACTED]
- [REDACTED]
- [REDACTED]
- [REDACTED]
- [REDACTED]
- [REDACTED]

---

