#### Non-measurable Disease

All other lesions (or sites of disease), including small lesions (longest diameter  $\geq 10$  to  $< 15$  mm with conventional techniques or  $< 10$  mm using spiral CT scan), are considered non-measurable disease.

Leptomeningeal disease, ascites, pleural, or pericardial effusion, inflammatory breast disease, lymphangitic involvement of skin or lung, abdominal masses/abdominal organomegaly identified by physical examination that is not measurable by reproducible imaging techniques are all non-measurable.

Bone lesions:

- Bone scan, PET scan, or plain films are not considered adequate imaging techniques to measure bone lesions. However, these techniques can be used to confirm the presence or disappearance of bone lesions
- Lytic bone lesions or mixed lytic-blastic lesions, with identifiable soft tissue components, that can be evaluated by cross sectional imaging techniques such as CT or MRI can be considered as measurable lesions if the soft tissue component meets the definition of measurability described above.
- Blastic bone lesions are non-measurable.

Cystic lesions:

- Lesions that meet the criteria for radiographically defined simple cysts should not be considered as malignant lesions (neither measurable nor non measurable) since they are, by definition, simple cysts.
- ‘Cystic lesions’ thought to represent cystic metastases can be considered as measurable lesions, if they meet the definition of measurability described above. However, if non cystic lesions are present in the same patient, these are preferred for selection as target lesions.

Lesions with prior local treatment:

- Tumor lesions situated in a previously irradiated area, or in an area subjected to other locoregional therapy, are usually not considered measurable unless there has been demonstrated progression in the lesion. Trial protocols should detail the conditions under which such lesions would be considered measurable.

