## GUIDELINES FOR EVALUATION OF MEASURABLE DISEASE

All measurements should be recorded in metric notation, using calipers if clinically assessed. All baseline evaluations should be performed as close as possible to the treatment start and never more than 4 weeks before the beginning of the treatment.

The same method of assessment and the same technique should be used to characterize each identified and reported lesion at baseline and during follow-up. Imaging based evaluation should always be done rather than clinical examination unless the lesion(s) being followed cannot be imaged but are assessable by clinical examination.

**CT, MRI:** CT is the best currently available and reproducible method to measure lesions selected for response assessment. This guideline has defined measurability of lesions on CT scan based on the assumption that CT slice thickness is 5 mm or less. As is described in Appendix II of the original source article cited above, when CT scans have slice thickness greater than 5 mm, the minimum size for a measurable lesion should be twice the slice thickness. MRI is also acceptable in certain situations (e.g., for body scans).

**Endoscopy, laparoscopy:** The utilization of these techniques for objective tumor evaluation is not advised. However, they can be useful to confirm complete pathological response when biopsies are obtained or to determine relapse in trials where recurrence following complete response or surgical resection is an endpoint.

**Cytology, histology:** These techniques can be used to differentiate between PR and CR in rare cases if required by protocol (for example, residual lesions in tumor types such as germ cell tumors, where known residual benign tumors can remain). When effusions are known to be a potential adverse effect of treatment (e.g., with certain taxane compounds or angiogenesis inhibitors), the cytological confirmation of the neoplastic origin of any effusion that appears or worsens during treatment can be considered if the measurable tumor has met criteria for response or stable disease in order to differentiate between response (or stable disease) and progressive disease.

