### **Evaluation of Best Overall Response**

The best overall response is the best response recorded from the start of the study drug treatment until the end of treatment taking into account any requirement for confirmation. On occasion a response may not be documented until after the end of therapy so protocols should be clear if post-treatment assessments are to be considered in determination of best overall response. Protocols must specify how any new therapy introduced before progression will affect best response designation. The patient's best overall response assignment will depend on the findings of both target and non-target disease and will also take into consideration the appearance of new lesions. Furthermore, depending on the nature of the trial and the protocol requirements, it may also require confirmatory measurement. Specifically, in non-randomized trials where response is the primary endpoint, confirmation of PR or CR is needed to deem either one the "best overall response".

The best overall response is determined once all the data for the patient are known. Best response determination in trials where confirmation of complete or partial response IS NOT required: Best response in these trials is defined as the best response across all time points (for example, a patient who has SD at first assessment, PR at second assessment, and PD on last assessment has a best overall response of PR). When SD is believed to be best response, it must also meet the protocol specified minimum time from baseline. If the minimum time is not met when SD is otherwise the best time point response, the patient's best response depends on the subsequent assessments. For example, a patient who has SD at first assessment, PD at second and does not meet minimum duration for SD, will have a best

response of PD. The same patient lost to follow-up after the first SD assessment would be considered invaluable.

Target Lesions	Non-target Lesions	New Lesions	Overall Response
CR*	CR	No	CR
CR	Non-CR/non-PD	No	PR
CR	Not evaluated	No	PR
PR	Non-PD or not all evaluated	No	PR
SD	Non-PD or not all evaluated	No	SD
Not all evaluated	Non-PD	No	NE
PD	Any	Yes or No	PD
Any	PD	Yes or No	PD
Any	Any	Yes	PD

\* CR = complete response; PR = partial response; SD = stable disease; PD = progressive disease; and NE = invaluable. See text for more details.

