7.2 Objective Response Rate (ORR)

The ORR will be estimated by the number of patients with a best overall response of CR or PR divided by the total number of patients who are evaluable for efficacy. The best overall response is the best response recorded from the start of the treatment until progression of disease, EOT, or until the patient commences further anti-cancer treatment, whichever comes first.

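### No readable rule covers a target lesion irradiated after its baseline measurement, so radiation shrinkage could count towards the Part 2 primary ORR

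*Protocol*

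**What the plan says.** **During treatment.** Protocol 8.5.2 says "Palliative radiotherapy may be given as described above". The next item in the same list excludes it from the prohibited therapies: "radiotherapy (other than palliative radiotherapy for symptom control) is not allowed concomitantly with the administration of study treatment". The readable text does not limit it to non-target lesions. The sections just before (8.5 and 8.5.1) do not mention radiotherapy, and the only earlier readable text on it is the pre-dose exclusion.

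**Before dosing.** Protocol 7.2, criterion 1, excludes "Radiotherapy with a limited field of radiation for palliation within 1 week of the first dose of study treatment". Protocol Appendix 3 says baseline evaluations should be as close as possible to treatment start and "never more than 4 weeks before the beginning of the treatment".

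**Scoring.** Under Appendix 3, PR is a fall of at least 30% in the sum of target-lesion diameters from baseline. SAP 7.1.1 builds each time-point response from the investigator's lesion assessments. SAP 7.2 takes the best response from the start of treatment "until progression of disease, EOT, or until the patient commences further anti-cancer treatment, whichever comes first". Protocol 10.1.1 stops tumor assessment at the same three events. ORR is the Part 2 primary endpoint (Protocol 5.3.2.1).

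**Irradiated lesions.** Appendix 3 (repeated in SAP Appendix 2) says lesions in a previously irradiated area "are usually not considered measurable unless there has been demonstrated progression in the lesion", and adds: "Trial protocols should detail the conditions under which such lesions would be considered measurable". On treatment begun before progression it says: "Protocols must specify how any new therapy introduced before progression will affect best response designation". The readable protocol and SAP answer neither request for palliative radiotherapy.

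**The concern.** Part 2 has no control arm and response is read by the investigator. If a target lesion shrinks because it was irradiated, no comparison cancels the effect, and the patient can be counted as responding to BBT-176. The response bias runs upward only. DoR (SAP 7.3) would then start from the same response.

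There are two routes:

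- **On treatment:** a target lesion is irradiated for symptoms while the patient stays on BBT-176.
- **Before dosing:** a lesion is measured at baseline, then irradiated more than a week before the first dose, and keeps its pre-radiation diameter as the reference.

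**Working it through.** The plan gives no figure to reproduce. Part 2 has no efficacy hypothesis (Protocol synopsis, Statistical Methods) and its size is redacted. The numbers below show what the rules allow, not what is expected.

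**1. Gap before dosing.** Oldest permitted baseline scan: 28 days before treatment. Radiotherapy exclusion: the last 7 days. Gap = 28 − 7 = up to 21 days in which a measured lesion can be irradiated. The trial's own screening window is redacted and may be shorter.

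**2. When one irradiated lesion is enough for PR.** With the other target lesions unchanged, the share of the baseline sum it must hold is 0.30 / (fractional shrinkage of that lesion).

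| Shrinkage of irradiated lesion | Share of baseline sum needed |
|---|---|
| 30% | 100% |
| 50% | 60% |
| 70% | 43% |
| 100% | 30% |

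Example: lesions of 40 mm and 20 mm, sum 60 mm. The first is halved to 20 mm and the second does not change. New sum 40 mm; change = (40 − 60)/60 = −33.3%, a PR. Here the irradiated lesion holds 40/60 = 67% of the sum, so the example suits the point. If the shrinkage lasts to the next 6-weekly scan, the response is also confirmed.

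**3. Effect of one such patient on ORR.** One response is worth 100/n points. Protocol 12.8 gives 12 (a review trigger per subgroup) and 30 (a ceiling per cohort) for the Part 1 RP2D exploratory cohorts. I use them as an assumed range: 100/12 = 8.3 points and 100/30 = 3.3 points. At an assumed n = 60 it is 1.7 points. SAP 7.7 asks for 80% intervals; the readable text names no method, so exact Clopper-Pearson is assumed.

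| Responders | ORR | 80% CI |
|---|---|---|
| 2/12 | 16.7% | 4.5 to 38.6% |
| 3/12 | 25.0% | 9.6 to 47.5% |
| 6/30 | 20.0% | 10.9 to 32.5% |
| 7/30 | 23.3% | 13.5 to 36.1% |

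**4. Upper bound.** Let q be the share of patients with an irradiated target lesion. If all of them counted as responders, the inflation would be q × (1 − true ORR). The documents give no q. Assuming q of 5% to 15% and a true ORR of 10% to 30%, it runs from 0.05 × 0.70 = 3.5 points to 0.15 × 0.90 = 13.5 points. Not every irradiated lesion will produce a PR, so the real effect would be smaller.

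**5. The two readings of the response window.**

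- *Palliative radiotherapy counts as further anti-cancer treatment.* The on-treatment route closes. But Protocol 10.1.1 then also ends tumor assessment, while 6.3.1 keeps the patient on BBT-176 until RECIST progression, which would no longer be looked for on schedule. Radiotherapy before the first dose is untouched.
- *It does not count.* Both routes stay open.

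Neither reading settles the matter.

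**The case against.** **Redaction.** A rule could sit in blacked-out text: the later items of Protocol 8.5.2, parts of 10.1.1 and 11.6.1, and SAP 5, 7.1.1, 7.1.2 and 7.6. The passage that 8.5.2 points back to may be hidden too. This stands. The claim is limited to the readable text, and if a rule exists the sponsor need only cite it.

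**RECIST already handles irradiated lesions.** A reader might infer that the plan never removes them. The documents do not support that: both appendices make previously irradiated lesions usually non-measurable unless they have progressed. But that rule governs which lesions are selected at baseline, not a lesion irradiated after its baseline measurement.

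**The response window may already close.** A reader might infer that the plan, followed as written, credits radiation effects to BBT-176. That is also too strong. The cut-off in Protocol 10.1.1 and SAP 7.2 is not restricted to systemic therapy, whereas the safety follow-up footnote in the Schedule of Activities is, so the wider wording can be read to include radiotherapy. The fault is an undefined term, and defining it does not deal with the pre-dose route.

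**The pre-dose route is only possible.** The 4 weeks is a maximum in reproduced RECIST text, and the scan may follow the radiotherapy. This stands.

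**The size is unknown.** Frequency is not documented, many bone lesions are not measurable under Appendix 3 and so cannot be target lesions, and Part 2 is descriptive, so no decision threshold is crossed. This stands, and it lowers the priority. Confirmation of response does not remove the problem, because radiation shrinkage can persist to the next scan.

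**Conclusion.** The point holds on the readable text, with medium confidence. Radiotherapy to a target lesion is not ruled out after the baseline measurement, either on treatment or, possibly, in the weeks before dosing. No readable rule says how such a lesion is scored, and the cut-off for best response leaves permitted palliative radiotherapy undefined. Radiation shrinkage could therefore enter the Part 2 primary ORR and DoR.

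The size per affected patient is 8.3 points at n = 12 and 3.3 at n = 30, both assumed sizes. The number of affected patients cannot be derived from the documents. The priority lies between worth considering and should be done: the effect may be small, but the repair is cheap and protects the primary endpoint.

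**What to change.** These are analysis and assessment changes only. They do not alter who may receive radiotherapy.

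1. **SAP 7.1.1 and 7.2.** Once a target lesion has been irradiated after baseline, later time points cannot be CR or PR; progression still counts. Any response, including its confirmation, must rest on scans before the radiotherapy date.
2. **Radiotherapy between baseline scan and first dose.** Do not count the patient as a responder if a target lesion was irradiated in that gap, unless the lesion was re-measured at baseline after the radiotherapy and had progressed.
3. **Denominator.** Keep all such patients in the ORR denominator as non-responders. SAP 7.2 divides by patients evaluable for efficacy, and no definition of that set is readable. If a non-evaluable patient dropped out, the remedy could raise ORR: 2/12 = 16.7% would become 2/11 = 18.2%.
4. **Response window.** State in Protocol 10.1.1 and SAP 7.2 whether palliative radiotherapy counts as further anti-cancer treatment, and that tumor assessment continues after it.
5. **Listing.** List responders who received palliative radiotherapy, with site and date.
6. **Cross-reference.** Reconcile the reference back in Protocol 8.5.2 with the passage it means. If a redacted passage already holds a rule, cite it.

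Cost: SAP wording and a short protocol clarification, with no extra patients and no scans beyond the existing schedule. SAP 6.4 already records non-drug treatments and procedures from 28 days before dosing; the eCRF must capture the irradiated site. The downside is a few more non-evaluable time points and possibly a slightly lower ORR.
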